5.3. Safety Set

The Safety Set consists of all randomized participants who received any study vaccination. The Safety Set will be used for analysis of safety except for the solicited ARs.

Subjects will be analyzed according to the vaccination group a subject received, rather than the vaccination group to which the subject is randomized to. Subjects who receive a vaccination/injection that is different from the vaccination/injection which the subject is randomized to will be summarized under the highest dose of vaccination group (i.e., mRNA-1647 **CCI** > mRNA-1647 **CCI** > mRNA-1647 **CCI** > Placebo).

5.4. Full Analysis Set

Full Analysis Set (FAS) for Antibody-Mediated Immunogenicity

The FAS for antibody-mediated immunogenicity consists of all randomized participants who

- a) receive any study vaccination,
- b) have baseline (Day 1) antibody-mediated immunogenicity data available for those analyses that require baseline data, and
- c) have at least one post-vaccination antibody-mediated immunogenicity assessment for the analysis endpoint.

FAS for Cell-Mediated Immunogenicity

The FAS for cell-mediated immunogenicity (CMI) consists of all randomized participants who

- a) receive any study vaccination,
- b) have baseline (Day 1) CMI data available for those analyses that require baseline data, and
- c) have at least one post-vaccination CMI assessment for the analysis endpoint.

Participants will be included in the vaccination group to which they are randomized.

5.5. Per-Protocol Sets

The Per-Protocol (PP) Set for Antibody-Mediated Immunogenicity

PP Set for Antibody-Mediated Immunogenicity consist of all FAS participants who

- a) comply with the vaccination schedule,
- b) comply with the timings of immunogenicity blood sampling to have post-vaccination results available for at least one assay component corresponding to the immunogenicity analysis objective (antibody-mediated immunogenicity endpoints), and
- c) have no major protocol deviations that impact immune response during the period corresponding to the immunogenicity analysis objective (antibody-mediated immunogenicity endpoints).

Subjects who were CMV seronegative at Screening and became CMV seropositive at baseline (before or on 1st dose of study vaccination) will be excluded from the PP Set for Antibody-Mediated Immunogenicity.

The PP Set for Antibody-Mediated Immunogenicity will serve as the primary population for the analysis of antibody-mediated immunogenicity data in this study. Participants will be included in the vaccination group to which they are randomized.

PP Set for CMI

PP Set for CMI consist of all FAS for Cell-Mediated participants who

- a) comply with the 3-dose vaccination schedule,
- b) comply with the timings of immunogenicity blood sampling to have post-vaccination results available for at least one assay component corresponding to the immunogenicity analysis objective (CMI endpoints), and
- c) have no major protocol deviations that impact immune response during the period corresponding to the immunogenicity analysis objective (CMI endpoints).

Subjects who were CMV seronegative at Screening and became CMV seropositive at baseline (before or on 1st dose of study vaccination) will be excluded from the PP Set for CMI.

The PP Set for CMI will serve as the primary population for the analysis of CMI data in this study. Participants will be included in the vaccination group to which they are randomized.

6. Statistical Analysis

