## **8.8. Sampling for Safety and Immunogenicity Assessments**

Detailed instructions for the collection, handling, and processing of samples are provided in the Laboratory Manual and Collection Flow Chart. The approximate blood volumes to be collected from each participant during the study are provided in [Table 2](#).

Participants will have 12 blood draws over the course of the trial to assess for eligibility, safety, and immunogenicity to mRNA-1647 vaccine.

Blood samples for screening laboratory testing will be collected at the Screening visit. Blood samples for safety laboratory assessments will be collected at Day 1, Day 8, Day 29, Day 56, Day 63, Day 84, Day 168, Day 175, and Day 196. Blood samples for antibody-mediated immunogenicity will be collected at Day 1, Day 29, Day 56, Day 84, Day 168, Day 196, Day 336, and Day 504. Blood samples for cell-mediated immunogenicity will be collected at Day 1, Day 8, Day 56, Day 63, Day 168, Day 175, Day 336, and Day 504. Blood for cell-mediated immunogenicity will be collected for a subset of up to 16 participants (approximately 8 CMV-

seropositive and 8 CMV-seronegative) for each dose level. The Sponsor will allocate clinical sites to enroll participants in this subset.

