4.1. Overall Study Design

This is a Phase 2, randomized, placebo-controlled, observer-blind, dose-finding trial enrolling healthy participants 18-40 years of age.

A schematic of the study design is shown in [Figure 1](#).

Figure 1 Study Design Schematic

Abbreviations: IST= internal safety team; mRNA = messenger ribonucleic acid.

In protocol amendment version 3, Part 2 of the study was added to evaluate the safety and immunogenicity of the selected CCI mRNA-1647 dose level in a larger female population, which is the target population for Phase 3 development.

CMV-seronegative and CMV-seropositive groups will be enrolled at the same time. Randomization will be stratified by CMV serostatus (via an Interactive Response Technology [IRT]) in a sequential manner into the CCI dose levels in Part 1 and the CCI dose level in Part 2. At each dose level, participants will be randomized in 3:1 ratio to either mRNA-1647 vaccine or placebo, administered in a 3-vaccination (0, 2, 6-month) schedule.

Treatment Arms

Part 1 CMV-seronegative Group (males and females aged 18-40 years)

- Approximately 60 participants randomized 3:1 to receive either CCI of mRNA-1647 vaccine or placebo in a 0, 2, 6-month schedule
- Approximately 60 participants randomized 3:1 to receive either CCI of mRNA-1647 vaccine or placebo in a 0, 2, 6-month schedule

- Approximately 60 participants randomized 3:1 to receive either CCI of mRNA-1647 vaccine or placebo in a 0, 2, 6-month schedule

Part 1 CMV-seropositive Group (males and females aged 18-40 years)

- Approximately 24 participants randomized 3:1 to receive either CCI of mRNA-1647 vaccine or placebo in a 0, 2, 6-month schedule
- Approximately 24 participants randomized 3:1 to receive either CCI of mRNA-1647 vaccine or placebo in a 0, 2, 6-month schedule
- Approximately 24 participants randomized 3:1 to receive either CCI of mRNA-1647 vaccine or placebo in a 0, 2, 6-month schedule

Part 2 CMV-seronegative Group (females aged 18-40 years)

- Approximately 80 participants randomized 3:1 to receive either CCI of mRNA-1647 vaccine or placebo in a 0, 2, 6-month schedule

Part 2 CMV-seropositive Group (females aged 18-40 years)

- Approximately 120 participants randomized 3:1 to receive either CCI of mRNA-1647 vaccine or placebo in a 0, 2, 6-month schedule

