6.4. Immunogenicity Analysis

The analyses of immunogenicity will be based on the PP Set and will be by serostatus group (ie, CMV-seropositive and CMV-seronegative groups) and vaccination group as defined in [Section 6.1](#). If the number of participants in the FAS and PP Set differ (defined as the difference divided by the total number of participants in the PP Set) by more than 10% (for each serostatus group), supportive analyses of antibody-mediated immunogenicity may be conducted using the FAS. The supportive analysis is required if the condition is met at end of study; it is optional for the interim analyses.

The GMT will be calculated using the following formula:

$$10^{\left\{ \frac{\sum_{i=1}^n \log_{10}(t_i)}{n} \right\}}$$

where t_1, t_2, \dots, t_n are n observed immunogenicity titers.

The geometric mean ratio (GMR) measures the changes in immunogenicity titers within subjects. The GMR will be calculated using the following formula:

$$10^{\left\{ \frac{\sum_{i=1}^n \log_{10}\left(\frac{v_{ij}}{v_{ik}}\right)}{n} \right\}} = 10^{\left\{ \frac{\sum_{i=1}^n \log_{10}(v_{ij}) - \log_{10}(v_{ik})}{n} \right\}}$$

where, for n subjects, v_{ij} and v_{ik} are observed immunogenicity titers for subject i at time points j and k , $j \neq k$

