6.4.1. Immunogenicity Assessments

There will be two types of immunogenicity assessments:

- Antibody-mediated immunogenicity assessments include serum neutralizing anti-CMV antibodies, anti-gB IgG, and anti-Pentamer IgG.
- CMI assessments include gB-specific and Pentamer-specific CD4 and CD8 cytokine secreting T-cells as measured by ICS. Blood for CMI will be collected for a subset of up to 16 participants (approximately 8 CMV-seropositive and 8 CMV-seronegative) for each dose level. Other exploratory CMI assessments may be performed.

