6.4.3. Analysis of CMI Endpoints

Descriptive summary statistics for the observed and change from baseline will be provided at each scheduled visit by serostatus group (ie, CMV-seropositive and CMV-seronegative groups) and vaccination group for CMI parameters, based on the PP Set for CMI. Descriptive statistics for the observed and change from baseline values will be plotted over time.

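### Cell-mediated immunity summaries admit only participants compliant with all three doses, even at visits before dose 3, and no FAS summary is planned to show the rest

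*SAP*

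**What the plan says.** SAP 5.5 sets three conditions for the PP Set for CMI. The first is to "comply with the 3-dose vaccination schedule", with no limit to a visit or period. The third, on major deviations, is limited to the period of the CMI objective. The antibody PP Set in the same section asks participants to "comply with the vaccination schedule" and does not mention three doses.

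SAP 6.4.3 plans descriptive statistics and plots of observed values and changes from baseline at each scheduled visit, "based on the PP Set for CMI". No other analysis set is named for CMI.

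SAP 6.4 provides a fallback when the FAS and PP Set differ by more than 10%: "supportive analyses of antibody-mediated immunogenicity may be conducted using the FAS". That wording leaves CMI out. SAP 5.4 nevertheless defines a separate FAS for CMI, and SAP Appendix B gives CMI visit windows for participants who had only the first dose or only the first two. Protocol Tables 6 and 7 schedule CMI blood draws for such participants.

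**The concern.** A result at Day 8 cannot depend on whether dose 3 was later given on schedule, and the same holds for every sample drawn up to and including the pre-dose sample at Month 6. Requiring compliance with dose 3 at these visits removes valid observations without making the remaining ones more faithful to the protocol.

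The CMI subset is the smallest in the trial, so losing one participant is visible in a group summary. The plan offers no second summary in which the excluded early results can be seen. The SAP also defines an analysis set and visit windows for partly vaccinated participants that no planned CMI summary uses, which suggests an omission and not a deliberate choice.

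**Working it through.** **Inputs**

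- Subset size: "subset of up to 16 participants (approximately 8 CMV-seropositive and 8 CMV-seronegative) for each dose level" (SAP 6.4.1).
- Allocation: "At each dose level, participants will be randomized in 3:1 ratio to either mRNA-1647 vaccine or placebo" (SAP 4.1).
- CMI draws: "Day 1, Day 8, Day 56, Day 63, Day 168, Day 175, Day 336, and Day 504" (Protocol 8.8). Draws on vaccination days are taken before the injection (Protocol 8.8.4), and SAP Appendix B labels the Month 6 CMI window as before the third dose.
- Non-compliance with the 3-dose schedule, *d*: not given. Assumed 10-20%.

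The documents state no sample size or precision for CMI. The allocation ratio can be checked against SAP 4.2: 252 × 3/4 = 189 on vaccine in Part 1, as stated.

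**Step 1: draws that precede dose 3.** Days 1, 8, 56, 63 and 168 make 5 of the 8 draws. Leaving out baseline, it is 4 of 7.

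**Step 2: group size.** Per serostatus and dose level, 8 × 3/4 = 6 on vaccine and 8 × 1/4 = 2 on placebo. SAP 6.1 pools placebo and adds a Total vaccine group. From Part 1 alone these are 3 × 2 = 6 and 3 × 6 = 18 per serostatus. The figure of 6 is an expectation: the subset is filled by site and no stratification within it is described. Under simple binomial allocation, exactly 6 of 8 has probability 28 × 0.75⁶ × 0.25² = 31%.

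**Step 3: chance that a group of 6 loses participants.** With independent non-compliance, expected n = 6(1 − d), P(≥1 lost) = 1 − (1 − d)⁶, and P(≥2 lost) = 1 − (1 − d)⁶ − 6d(1 − d)⁵.

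| d (assumed) | Expected n | P(≥1 lost) | P(≥2 lost) |
|---|---|---|---|
| 10% | 5.4 | 47% | 11% |
| 15% | 5.1 | 62% | 22% |
| 20% | 4.8 | 74% | 34% |

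**Step 4: what a loss costs.** As a gauge only, since SAP 6.4.3 plans no interval for CMI, take the 95% half-width of a mean in SD units, t(0.975, n − 1)/√n. It is 1.05 at n = 6, 1.24 at n = 5 (+18%) and 1.59 at n = 4 (+52%).

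**Step 5: how much could be recovered.** Step 3 counts everyone who fails the 3-dose criterion, so it is an upper bound on what another summary could restore.

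- *Day 63.* A participant who misses dose 2 has no scheduled draw then. Protocol Table 7 has none, and Protocol 7.1 replaces these visits with safety calls until Month 6. If half of the assumed non-compliers have missed dose 2 or left the study by then (illustrative), the remaining rate is 5-10%. The chance of at least one recoverable loss is then 1 − 0.95⁶ = 26% to 1 − 0.90⁶ = 47%.
- *Month 6.* Participants followed under Protocol Table 6 have a telephone call at Day 168. A Month 6 sample exists only for those who attended and were sampled, or who were followed under Table 7.

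**The case against.** The strongest reply is that little depends on this. CMI is exploratory, nothing is tested (SAP 4.2), and SAP 6.1 and 6.4.3 plan only n, mean, SD, median, minimum and maximum. No planned interval widens. Groups of 6 and 2 are not the whole picture, because placebo is pooled, a Total vaccine group is reported, and SAP 6.5 combines Parts 1 and 2. The documents do not say whether Part 2 adds to the CMI subset at its dose. All of this stands and limits the importance of the point.

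Several stronger readings are tempting and should be resisted:

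- *That the data are discarded.* SAP 6.5 plans individual listings in the clinical study report. The data are missing from summaries, not from the report.
- *That early CMI results are biased.* Selection on later attendance or tolerance is possible, but nothing in the documents links CMI response to missing dose 3.
- *That the CMI rule is stricter in practice than the antibody rule.* The protocol has one schedule, of three vaccinations, so the two wordings may operate alike.
- *That any delay in dose 3 removes early data.* Schedule compliance is not defined operationally, and SAP 6.2.6 leaves the major deviation rules to be finalised before database lock.
- *That the PP Set should be redefined visit by visit.* A fixed cohort keeps the same people along each plotted trajectory, which matters in groups this small. SAP 6.5 also records that sponsor members saw individual listings at the 7-month interim analyses. Changing the primary CMI population after that carries an integrity cost.

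Protocol 9.6.3 does allow supportive FAS analyses of immunogenicity in general. That does not close the gap: it is optional, SAP 6.4 narrows it to antibodies, and SAP Section 1 says the SAP prevails.

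**Conclusion.** The point holds as a gap in the planned summaries of an exploratory endpoint. Criterion (a) in SAP 5.5 has no limit by visit, SAP 6.4.3 uses that set throughout, and 4 of the 7 post-baseline CMI draws come before dose 3. Participants who do not comply with dose 3 are therefore absent from the tables and plots of results that dose 3 could not have affected, and no planned summary on the FAS for CMI shows them.

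The number affected is unknown. The range of 47-74% for a group of 6 rests on an assumed 10-20% non-compliance, independence between participants and a derived group size. It is a ceiling, and the recoverable part is smaller at Day 63 and Month 6. No primary or secondary conclusion changes. This is a cheap improvement and not a flaw that threatens the trial.

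**What to change.** Keep the PP Set for CMI as the primary CMI population. Amend SAP 6.4 and 6.4.3 so that the same CMI descriptive summaries and plots are also provided by visit, serostatus and vaccination group on the FAS for CMI that SAP 5.4 already defines, using the Appendix B windows and showing n at each visit.

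Preferably do not tie this to the 10% trigger. With 3 × 8 = 24 CMI participants per serostatus in Part 1, two exclusions give 2/22 = 9.1%, just below it.

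The cost is one additional set of tables and figures. Since n and membership vary by visit on the FAS, its plots should be read as supportive beside the fixed PP cohort. No new data, change in trial conduct or redefinition of the primary CMI population is needed, and SAP version 5.0 is written ahead of the final database lock.

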6.1. General Considerations

The Schedule of Assessments is provided in the protocol Table 1 for subjects completing all vaccinations, Table 6 for subjects completing the first 2 vaccinations only, and Table 7 for subjects who completing the first vaccination only.

Continuous variables will be summarized using the following descriptive summary statistics: the number of subjects (n), mean, standard deviation (SD), median, minimum (min), and maximum (max).

Categorical variables will be summarized using counts and percentages.

Baseline value, unless specified otherwise, will be defined as the most recent non-missing measurement (scheduled or unscheduled) collected before the first dose of study vaccination.

For the summary statistics of all numerical variables unless otherwise specified, the display precision will follow programming standards. Please see [Appendix A](#) for variable display standards.

When count data are presented, the percentage will be suppressed when the count is zero in order to draw attention to the non-zero counts. A row denoted “Missing” will be included in count tabulations where specified on the shells to account for dropouts and missing values. The denominator for all percentages will be the number of subjects in that vaccination group within the analysis set of interest, unless otherwise specified.

Study day relative to the first vaccination will be calculated as below:

- a) study day prior to the first vaccination will be calculated as: date of assessment/event – date of the first vaccination;
- b) study day on or after the date of the first vaccination will be calculated as: date of assessment/event – date of the first vaccination + 1;

Study day relative to the most recent vaccination will be calculated as below:

- a) study day prior to the first vaccination will be calculated as: date of assessment/event – date of the first vaccination;
- b) study day on or after the date of the first vaccination but before the second vaccination (if applicable) will be calculated as: date of assessment/event – date of the first vaccination + 1;
- c) study day after the date of the second vaccination but before the third vaccination (if applicable) will be calculated as: date of assessment/event – date of the second vaccination + 1; if study day is on the same day as the second vaccination, date and time will be compared with the second vaccination date and time. If it is prior to the second vaccination, then study day is calculated as [b\)](#); If it is after the second vaccination or the time is missing or not available, then study day is calculated as: date of assessment/event – date of the second vaccination + 1. If a subject did not receive the second vaccination, but received the third vaccination, study day after the second vaccination will be treated as missing, and only calculate in relative to the third vaccination.

- d) study day after the date of the third vaccination will be calculated as: date of assessment/event – date of the third vaccination + 1; if study day is on the same day as the third vaccination, date and time will be compared with the third vaccination date and time. If it is prior to the third vaccination, then study day is calculated as: date of assessment/event – date of the second vaccination + 1; If it is after the third vaccination or the time is missing or not available then study day is calculated as: date of assessment/event – date of the third vaccination + 1.

For GMT calculation, antibody values reported as below the lower limit of quantification (LLOQ) will be replaced by $0.5 \times \text{LLOQ}$. Values that are greater than the upper limit of quantification (ULOQ) will be converted to the ULOQ. Missing results will not be imputed.

The following **stages** are used for reporting and analysis purposes:

- Vaccination stage:

For assessments that will be collected throughout the study (eg, unsolicited AE), it consists first vaccination on Day 1 to the earliest date of (28 days after last vaccination [ie, the day of last vaccination and 27 subsequent days], discontinuation from the study, or death). If a subject receives three vaccinations, this stage starts at the first vaccination on Day 1 and continues through the earliest date of (28 days after 3rd vaccination, withdraw from study, or death).

For assessments that will be collected at study visits (eg. laboratory and vital sign), if a subject receives three vaccinations, this stage starts at the first vaccination on Day 1 and continues through the earliest date of (Month 7 visit, withdraw from study, or death); If a subject receives first two vaccinations, this stage starts at the first vaccination on Day 1 and continues through the earliest date of (Month 3 visit, withdraw from study, or death); If a subject receives first vaccination only, this stage starts at the first vaccination on Day 1 and continues through the earliest date of (Month 1 visit, withdraw from study, or death).

- Follow up stage: For assessments that will be collected throughout the study (eg, unsolicited AE), this stage starts at 29 days after the last vaccination (ie, the day of last vaccination and 28 subsequent days, regardless of number of vaccinations received) and continue until the earliest date of (study completion, discontinuation from the study, or death).

There is no planned follow up stage for assessments that will be collected at study visits (eg. laboratory and vital sign).

- Overall stage: This stage starts at the first vaccination on Day 1 and continues through the earliest date of (study completion, discontinuation from the study, or death).
- 28 days after each vaccination stage: This stage starts at the day of each vaccination and continue through the earliest date of (the day of each vaccination and 27 subsequent days, next vaccination (if applicable)).

Unscheduled visits: Unscheduled visit measurements will be included in analysis as follows:

- In scheduled visit windows per specified visit windowing rules.
- In the derivation of baseline/last on-treatment measurements.
- In the derivation of maximum/minimum on-treatment values and maximum/minimum change from baseline values for safety analyses.
- In individual subject data listings as appropriate.

Visit windowing rules: The analysis visit windows for protocol-defined visits are provided in [Appendix B](#).

Incomplete/missing data:

- Imputation rules for missing prior/concomitant medications, non-study vaccinations and procedures are provided in [Appendix C](#).
- Imputation rules for missing AE dates are provided in [Appendix D](#).
- For laboratory assessments, if majority of results are indefinite, imputation of these values will be considered. If the laboratory results are reported as below the LLOQ (eg, < 0.1), the numeric values will be imputed by $0.5 \times \text{LLOQ}$ in the summary. If the laboratory results are reported as greater than the ULOQ (eg, > 3000), the numeric values will be imputed by ULOQ in the summary.

Other incomplete/missing data will not be imputed, unless specified otherwise.

The following **vaccination groups** will be used for summary purposes:

- mRNA-1647 vaccine: **CCI**

- mRNA-1647 vaccine: CCI
- mRNA-1647 vaccine: CCI
- mRNA-1647 vaccine: Total
- Placebo

Summary by study part and CMV serostatus:

All analyses and data summaries/displays will be provided by CMV serostatus (CMV-seropositive and CMV-seronegative) unless otherwise specified. Analyses and data summaries/displays may be provided by study part (Part 1, Part 2, and/or overall) when specified, please also refer to [Section 6.5 Planned Analyses](#).

For those subjects who were CMV seronegative at Screening and became CMV seropositive at Baseline (before or on the day of 1st vaccination), the subjects will be:

- included in the Randomized Set under the CMV status group the subjects were randomized under, ie, CMV seronegative
- included in the Solicited Safety Set and Safety Set, under CMV seropositive group
- included in the FAS, under CMV seropositive group
- excluded from the PP Set for Antibody-Mediated Immunogenicity data and CMI data

All analyses will be conducted using SAS Version 9.4 or higher.

